**NCT05425966**

**Principal Investigator:** [name] [name] PhD

**IRB Study Title:** Remote School-Home Program to Improve Youth Attention and Behavior in Mexican Students

**IRB #:** 21-34748

**Reference #:** 321420

**Committee of Record:** San Francisco General Hospital Panel

**Most Recent Approval Date:** 08/22/2022

**Pages 2-6 of the current document:** Study Protocol

**Page 6 of the current document:** Statistical Analysis Plan

**STUDY PROTOCOL:** A total of  $N = 24$  youth with inattention and disruptive behavior will participate in a 3-school open-trial evaluating the web-based CLS-R-FUERTE program in the Sinaloa Public School District (i.e.,  $n = 8$  youth/school). Youth with attention/behavior concerns will be recruited via school-wide meetings at each participating school and teacher/school clinician referral. Parents and teachers of youth will provide informed consent and baseline ratings of ADHD/ODD; youth will provide assent; and school clinicians will be tested on their evidence based practice skills. Next, our team will train school clinicians and monitor fidelity, satisfaction and adherence during the 6-week program. Then we will collect post ratings from parents/teachers and test school clinicians again. We will make iterative updates to the program as indicated after observation/ feedback from each school (totaling 3 iterations). School clinicians, parents, and teachers will be compensated \$10 each time they complete ratings (\$20 total). Our team will iteratively update the web-based program and research protocol based on observations and participant feedback.

CLS-R-FUERTE is a 6-week intervention aimed at reducing attention and behavior symptoms in students. The intervention is based on CLS and includes a comprehensive and integrated student, parent and teacher component. Students presenting with attention and behavior problems at school sites without the CLS-R-FUERTE intervention may be referred to the usual care protocol of that school which may include individual therapy, social skills groups or referrals to the community.

**INCLUSION CRITERIA:** The open-trial across 3 schools in the Sinaloa Public School District will include  $N = 3$  School Clinicians (i.e., 1 per school);  $N = 24$  youth with inattention and disruptive behavior (i.e., 8 youth/school);  $N = 24$  parents (i.e., 1 per youth) and  $N = 24$  teachers (i.e., 1 per youth). School Clinicians at the required  $N = 3$  schools are recruited via annual conferences our team has held with the school district describing our preliminary results to-date. To qualify, school clinicians must speak Spanish, be employed as by a participating school, and be willing to engage in the training activities. Youth with attention/behavior concerns in grades 1-5 and their parents/teachers will be recruited via school-wide meetings at each participating school and teacher/school clinician referral. This is a procedure we've used successfully in our previous work in Sinaloa, Mexico. Specifically, we may invite all families and personnel at participating schools to a meet-and-greet. In this meet-and-greet, we introduce our study team and show a brief silent video depicting a youth with inattention and disruptive behavior. Families who identify with the families in the video can self-refer for a program screener with our team. Teachers or school clinicians also may refer families for a program screener with our team. We have used this recruitment strategy successfully in the CLS-FUERTE program pilot. To qualify, youth must demonstrate  $>6$  symptoms of inattention and/or  $>6$  symptoms of hyperactivity/

impulsivity rated by parents or teachers, and >1 domain of impaired functioning, on a screening with our study team). In addition, > 1 parent or caregiver (here-on referred to as “parent”) and > 1 teacher of the youth must speak Spanish and be willing/available to participate in sessions.

**EXCLUSION CRITERIA:** Anyone who does not speak and read Spanish will be excluded, given that all informed consent, measurement, and activity procedures will be conducted in Spanish.

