## ESTIMATED TIME COMMITMENT FOR PARTICIPANTS:

Youth: 6 60-minute sessions and 1-2 30-minute meetings (Total up to 7 hours)

Teachers: 1 1-hour session, 1-2 30-minute meetings, and up to 2-hours to fill out measures (Total up to 4 hours)

Parents: 6 90-minute sessions, 1-2 30-minute meetings, and up to 2-hours to fill out measures (Total up to 12 hours)

School clinicians: 6 60-minute child sessions, 6 90-minute parent sessions, 1 1-hour teacher sessions, up to 16 30-minute meetings, 9 hours of consultation, and up to 2-hours to fill out measures (Total up to 35 hours)

**STATISTICAL METHODS:** We will initially test the web-based CLS-R-FUERTE program in a 3-school open trial by examining if: 1) school clinician fidelity to intervention on the CORS reaches >80% of content delivered and >4 out of 5 quality rating; school clinicians' ratings on the satisfaction questionnaire reach >4 out of 5; school clinicians' ratings on the SUS reach >80%; and school clinicians' evidence based practice skills, knowledge, and attitudes on the KAB improve from pre to post using repeated-measures T-tests; 2) participant session attendance and engagement/adherence ratings reach >4 out of 5 on the CORS with a benchmark of at least 80%; DRC use reaches >3 out of 5 days; and SUS ratings reach >80%; as well as if improvements on youth outcomes improve from pre to post using repeated-measures T-tests. We will conduct analyses in SPSS. 3) Themes from observation and feedback from the open-trial will be incorporated with results above to inform iterative changes to the web-based program after each school.

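### Does updating the program after each school require the plan to specify benchmarks and pre-post tests by school or version?

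*Combined protocol and SAP*

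**What the plan says.** The Study Protocol section describes a three-school open trial in which the program is revised as it goes: "We will make iterative updates to the program as indicated after observation/ feedback from each school (totaling 3 iterations"). The same paragraph extends this beyond the program: "Our team will iteratively update the web-based program and research protocol based on observations and participant feedback". The Inclusion Criteria section sets the size at each site: "School Clinicians (i.e., 1 per school") and "i.e., 8 youth/school".

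The Statistical Methods paragraph, which serves as the SAP, opens with "We will initially test the web-based CLS-R-FUERTE program in a 3-school open trial by examining if". It then lists fidelity, satisfaction, usability, attendance and daily-report-card (DRC) benchmarks and two sets of pre-post comparisons. For clinicians the question is whether "evidence based practice skills, knowledge, and attitudes on the KAB improve from pre to post using repeated-measures T-tests"; for youth it is put "as well as if improvements on youth outcomes improve from pre to post using repeated-measures T-tests". No benchmark or test is given a school or version level. The third item says that themes from observation and feedback "will be incorporated with results above to inform iterative changes to the web-based program after each school".

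**The concern.** If the program changes between schools, the 24 youth do not all receive the same intervention, and a t-test over all of them estimates a mixture. That test ignores the order of the schools. A program that improves from version to version and one that deteriorates can give the same estimate and p-value, although improvement across versions is the purpose of iterating. The benchmarks could behave in the same way: if a percentage is averaged over clinicians, one poor school can sit behind a passing mean.

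There is also a question of what is being evaluated. If an update follows the third school, the version that leaves the trial was not used by anyone in it. A reader who took the combined result as the effect of that version would be wrong. The sentence about updating the research protocol has no stated limits, which raises the further worry that the data being combined might not be comparable.

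**Working it through.** **Inputs from the documents.** There are 3 schools, with 8 youth and 1 clinician in each: 3 × 8 = 24 youth and 3 × 1 = 3 clinicians, which match the stated totals. The plan gives no alpha, SD, effect size, power or dropout rate, so there is no power figure to reproduce. Everything below assumes two-sided alpha 0.05, within-school SD of change = 1, independent youth and complete post ratings. The effects are hypothetical.

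**1. Can a combined test hide the order?** Take school means of 0.9, 0.6 and 0.0.
- Combined mean = (0.9 + 0.6 + 0.0)/3 = 0.50.
- Total variance = [3 × 7 × 1 + 8 × (0.4² + 0.1² + 0.5²)]/23 = (21 + 3.36)/23 = 1.059, so SD = 1.029.
- t = 0.50 × √24/1.029 = 2.38 on 23 df, p = 0.026.
- The order 0.0, 0.6, 0.9 gives the same figures.

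So it can, but this is true of every pooled test and says nothing particular about this plan.

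**2. Would by-school figures reveal the pattern?** Use the same example.
- Half-width for one school: t(0.975, 7)/√8 = 0.84. For all 24: t(0.975, 23)/√24 = 0.42.
- Best school: 0.9 ± 0.84, or 0.06 to 1.74. Worst school: 0.0 ± 0.84, or −0.84 to 0.84. The intervals overlap widely.
- Test of school differences: F = (3.36/2)/1 = 1.68 on 2 and 21 df, p = 0.21.
- Power of that F-test for other assumed school effects: 16% for 0.3/0.6/0.9, 50% for 0/0.6/1.2 and 76% for 0/0.3/1.5.

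Only very large differences would stand out. A difference that did stand out could be due to the version, the school or its one clinician, and the design cannot separate these.

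**3. Clinician measures.** The KAB t-test has 3 clinicians and 2 df (critical t = 4.30, half-width 4.303/√3 = 2.48 SD). With one clinician per school no within-school test exists, so a version breakdown of this analysis is impossible. For SUS, hypothetical scores of 95, 90 and 60 average 245/3 = 81.7 and pass the 80% mark. The plan does not say that scores are averaged; if each clinician must pass, the 60 fails visibly.

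**4. What the text already provides.** The third item of Statistical Methods has results, together with themes, inform changes after each school. That can only be done if results are looked at as each school finishes. No section says that results will be reported only in combined form.

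**The case for a change.** The strongest case for a change is that it costs almost nothing. Because iteration is the purpose, a display by iteration is the natural one. A change log and by-school columns need no new data, and would show which version each figure describes. That the third item implies by-school review is not the same as committing to report it. All of this is fair, and a good trial report would include youth mean change by school, without tests, and a list of what was changed.

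It does not amount to a defect in the plan. The combined analysis would stay as it is, and no result or attributable conclusion would change. For clinician measures the display partly defeats itself: by-school fidelity, satisfaction, SUS and KAB values are one person's scores, and labelling schools by version is weak protection within a district where the order of schools may be known. Masking those cells removes much of the table.

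The open-ended sentence on research-protocol updates is the less comfortable part. No section proposes altering eligibility, measures or cut-offs midway. A clause freezing them would not be a clean remedy either: Inclusion Criteria does not state the Stage 3 screening rule that both parent and teacher must report impairment, and Statistical Methods does not name the youth outcome instruments. Those are separate matters that a by-version breakdown would not resolve.

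**Conclusion.** No change to the plan follows. The documents disclose that the program may change after each school, call the trial an initial open test, and route results back into development after each school. A combined pre-post result is then an average over the development series, and a competent analyst would describe it so and add that any version produced after the third school was not tested here. The plan's silence on a by-school table and a change log is a reporting detail.

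The gain from specifying a breakdown would be small: about ±0.84 SD per school against ±0.42 SD combined, with version inseparable from school and clinician. These half-widths assume independent youth, a common SD of change and no missing post ratings. With 6 of 8 post ratings per school they widen to 1.05 and 0.50. If youth within a school are correlated (assumed ICC 0.05 to 0.20, design effect 1 + 7 × ICC = 1.35 to 2.40) and only the 2 df from three schools are used, the combined half-width is 4.303 × √(1.35/24) = 1.02 to 4.303 × √(2.40/24) = 1.36 SD. Even the combined estimate is then a development-stage signal, and finer cuts of it could only be descriptive.

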### Parent and Teacher Participants

-Student of parent/teacher does not meet child inclusion/exclusion criteria above

-Parent or Teacher does not read or speak Spanish (inability to complete assessment measures or participate in group treatments)

**School Clinician Eligibility:** Any school clinician working in the participating Sinaloa school district.

**CHILD PARTICIPANT ELIGIBILITY:** Screening and confirmation of eligibility for youth will follow a three-stage (multiple-gated) procedure.

Stage 1) Involves identification of children by parent self-referral or staff clinicians at each participating school; children must be having academic and social problems related to inattention and/or hyperactivity/impulsivity.

Students who meet first stage entry criteria (e.g., age, grade, mainstream class placement, absence of significant visual or hearing impairment, severe language delay, psychosis, global intellectual impairment, or serious emotional disturbance requiring special education services, per school clinicians and school records, and living with a caretaker who is available to participate in treatment) will be invited to participate in screening.

Stage 2) Next, our program staff will initiate contact with families who self-referred or are referred by the school or referred families can contact our program staff themselves. Families will complete a screening (remote or in-person, depending on their preference) with our program staff about academic, social, and behavioral functioning at school and at home. Questions from the Developmental Family History Form and items from the Child Sympto Inventory-CSI are used to determine sufficient impairment. Parents of children who meet these criteria will be invited to the third stage of screening.

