Stage 3) During the final stage, parents complete the CSI, IRS, and Developmental History Form. Teachers also complete the CSI and IRS. After parents and teachers complete rating forms, judgements about eligibility at stage 3 will be made by UCSF program staff based on the interview and ratings provided by teachers and parents. To document ADHD symptom presence, we require six or more inattention symptoms and/or six or more hyperactive-impulsive symptoms endorsed by either the parent or teacher as occurring ‘often’ or ‘very often’. To document cross-situational impairment (and need for home and school treatment), we require impairment in at least one domain on the Impairment Rating Scale by both parent and teacher (score of 3 or greater). Committee on Human Research (CHR)-approved study descriptions are reviewed and families complete consent and assent forms. Those who consent will complete remaining baseline measures. we will then review all available data, including symptom counts and impairment, following DSM-V guidelines. Final determination of eligibility will be based on the child meeting all study criteria as determined by the PI.

**Parent Participant Eligibility:** Must have a child whom meets the above eligibility requirements. The parent must participate in the intervention.

**Teacher Participant Eligibility:** Must have a student whom is participating in the program. The teacher must be willing to participate in the intervention.

We have used these eligibility criteria successfully in the CLS-FUERTE program pilot.

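### Do the inclusion section and the Stage 3 eligibility rules admit different children?

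*Combined protocol and SAP*

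**What the plan says.** The child entry rules appear in several places in the combined protocol and SAP.

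- **Inclusion Criteria, symptoms:** "To qualify, youth must demonstrate $>6$ symptoms of inattention and/or $>6$ symptoms of hyperactivity", with the rating coming from parents or teachers.
- **Inclusion Criteria, impairment:** "impulsivity rated by parents or teachers, and >1 domain of impaired functioning, on a screening with our study team". No impairment informant, instrument or cut-off is named.
- **Inclusion Criteria, adults:** "In addition, > 1 parent or caregiver" and "> 1 teacher of the youth must speak Spanish and be willing/available to participate in sessions". The same section plans 24 parents and 24 teachers for 24 children, one of each per child.
- **Child Participant Eligibility, Stage 3, symptoms:** "we require six or more inattention symptoms and/or six or more hyperactive-impulsive symptoms endorsed by either the parent or teacher".
- **Child Participant Eligibility, Stage 3, impairment:** "we require impairment in at least one domain on the Impairment Rating Scale by both parent and teacher (score of 3 or greater".
- **Child Participant Eligibility, Stage 1:** children must be free of several conditions, among them "global intellectual impairment, or serious emotional disturbance requiring special education services". The Child Participants list under Exclusion Criteria names neither of these. It does exclude all-day special education placement and, in general terms, conditions incompatible with the treatment.

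The eligibility section presents these stages as one gated sequence. Program staff make the Stage 3 judgement, and the PI makes the final decision, which requires that every study criterion be met.

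**The concern.** As printed, the two statements of the rule differ at the boundary. A child with exactly six symptoms, or with one impaired domain from each informant, is eligible at Stage 3 and ineligible under the inclusion section. A child whose impairment is reported by one informant only fails Stage 3 but might pass the inclusion section, which does not say who must report it. A child with serious emotional disturbance and part-day special education services fails Stage 1 but meets no named exclusion.

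The study is a single-arm, pre-post comparison in 24 children, eight from each of three schools, so the entry rule defines whom the result describes. If schools applied different versions, the pooled sample would mix populations. Impairment both at home and at school, which Stage 3 gives as the reason for a combined program, might also not hold for every child.

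**Working it through.** The plan gives no figure to reproduce here. The check sets the rules side by side and applies both to the same profiles.

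**Step 1. What `>` means in the inclusion section.** Taken literally, the adult rule needs at least two parents and two teachers per child, so at least 2 × 24 = 48 of each. The same section plans 24 of each. The literal reading is therefore excluded by the section itself, and `>` in the adult rule must mean at least. The symptom and domain rules use the same sign in the same paragraph. As weaker support, Statistical Methods prints `>` thresholds for attendance and adherence beside a benchmark worded as a minimum of 80%.

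**Step 2. The rules side by side, with `>` as at least.**

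| Item | Inclusion Criteria | Stage 3 |
|---|---|---|
| Symptoms in either list | 6 or more | 6 or more |
| Symptom rater | parent or teacher | parent or teacher |
| Impaired domains | 1 or more | 1 or more |
| Impairment rater | not stated | parent and teacher |
| Instrument and cut-off | not stated | Impairment Rating Scale, 3 or greater |

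**Step 3. Enumeration.** Assume 0 to 9 symptoms in each of two lists and 0 to 3 impaired domains from each informant. The documents give neither range. This makes 10 × 10 × 4 × 4 = 1,600 profiles. They are logical cases, not children, and carry no frequency weights.

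- Symptoms: at least 6 in one list or both, 100 − 6 × 6 = 64 combinations; more than 6, 100 − 7 × 7 = 51.
- Stage 3 impairment, at least 1 domain from both: 3 × 3 = 9 combinations. Stage 3 admits 64 × 9 = 576.
- Inclusion section, at least 1 domain: 16 − 1 = 15 combinations if either informant suffices, 9 if both are needed.
- Inclusion section, more than 1 domain: 16 − 4 = 12 combinations if either suffices, 2 × 2 = 4 if both are needed.

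| Reading of the inclusion section | It admits | Passes both sections | Inclusion only | Stage 3 only |
|---|---|---|---|---|
| At least, both informants | 64 × 9 = 576 | 576 | 0 | 0 |
| At least, either informant | 64 × 15 = 960 | 576 | 384 | 0 |
| Strict, both informants | 51 × 4 = 204 | 204 | 0 | 372 |
| Strict, either informant | 51 × 12 = 612 | 408 | 204 | 168 |

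**Step 4. Who is enrolled.** Every criterion must be met, so the enrolled set is the column of profiles that pass both sections. With `>` as at least, that is 576 in both rows, exactly the Stage 3 set. The 384 profiles that only the inclusion section would admit have impairment from one informant, and Stage 3 stops them. The inclusion section's silence on the informant therefore changes nothing.

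**Step 5. The exclusion lists.** Only children who clear Stage 1 are invited to screening. Global intellectual impairment and serious emotional disturbance needing special education services are checked there, so a child with either does not go forward, whether or not the exclusion list repeats them.

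**Step 6. Screening load.** Suppose each informant independently reports impairment in a share p of symptomatic children, with p = 0.7, 0.8 or 0.9 (assumed). An either-informant rule admits 1 − (1 − p)² = 0.91, 0.96, 0.99. A both-informant rule admits p² = 0.49, 0.64, 0.81. Filling 24 places takes 24/0.91 = 26.4, 24/0.96 = 25.0 and 24/0.99 = 24.2 children under the first rule, and 24/0.49 = 49.0, 24/0.64 = 37.5 and 24/0.81 = 29.6 under the second. The arithmetic is sound, but the documents nowhere state an either-informant rule for impairment. The gap is between the Stage 3 rule and a hypothetical one.

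**The case for a change.** The strongest reply is that the requirement to meet every study criterion cannot cure a doubt about what the criteria are. If `>` were truly strict, the enrolled set in the table would shrink from 576 profiles to 408 or 204, and boundary children would be turned away. The inclusion section also refers to a screening with the study team, and Stage 2 describes such a screening, based on the developmental history form and symptom inventory items rather than the Impairment Rating Scale. Stage 1 relies on school clinicians and school records, with one clinician per school, and its list of conditions is introduced as examples. Finally, the Study Protocol section allows the research protocol to be updated between schools.

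Part of this stands. The printed signs do differ, and the sections would read better if one referred to the other. The rest does not carry the concern. The strict reading is ruled out for the adult rule by the planned numbers, and nothing suggests a different meaning two sentences earlier. A Stage 2 screen with a different instrument is an earlier gate, not a rival final rule. Local judgement at Stage 1 is a feature of the referral route and would remain with identical lists; the symptom and impairment thresholds are applied centrally. A later protocol update would be a new decision, not a result of the present wording.

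**Conclusion.** The concern does not hold as a defect in the plan. With `>` read as at least, the symptom and domain thresholds agree, and the enrolled set is the Stage 3 set: none of the 1,600 enumerated profiles is enrolled or refused differently because of the inclusion section's wording. The claims that two populations are enrolled, or that schools set their own thresholds, do not follow, because the gates are cumulative and the last is decided centrally. Both-informant impairment is secured for every enrolled child because each must pass Stage 3.

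This rests on two assumptions: that `>` in the inclusion section stands for at least, which its planned one parent and one teacher per child strongly support, and that all gates must be passed, which the eligibility section states. What remains is clerical: a sign to check against the source document, details given in one section and not repeated in the other, and two conditions listed at Stage 1 only. None of it alters the pre-post analysis or its interpretation.
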